a total of \$330. Participants will be compensated up to \$25 at Baseline, \$85 at Week 4, \$110 at Week 8 and \$110 at Week 12 study periods. Payments will be made using the Greenphire ClinCard to increase accountability and facilitate ease of payment. Participants will also be provided a study smartphone for the duration of their participation with paid service for 3 months so that they can immediately contact study staff for questions, receive reminders of upcoming appointments and study protocol, and complete EMAs and iCO tests. We will also facilitate study calls/visits by offering evening and weekend call times/appointments as well as additional retention strategies (e.g., multiple sources of contact, reminder calls/texts/emails). These methods are consistent with our team's previous studies and have resulted in excellent retention rates (>80%).^{75,87,88,90,99,100,104,105}

Detailed Study Procedures

Coach Calls: All study participants will receive three calls (~10-15 minutes) from trained tobacco cessation coaches at Time 0, +14 days, and +4 weeks. Prior to randomization, participants will complete the baseline assessment over the phone or online via REDCap. For participants randomized to JUUL, coaches will provide behavioral counseling and education on ECs, how to use and troubleshoot the JUUL device, and aid in helping the participant develop strategies to help them switch to JUUL. Coaches will also assess for JUUL usage at the +14 days and +4 week calls to help determine if the quantity of the study product that was mailed to the participant should be increased or decreased. For those randomized to NRT control, coaches will provide smoking cessation counseling grounded in social cognitive theory and the US PHS clinical guidelines. Specifically, cessation counseling will emphasize five keys to quitting tobacco: setting a quit date, using cessation medications, tobacco-proofing one's environment, coping with urges to smoke, and enlisting social support.¹⁰⁶

Baseline and Follow-up Assessments: All participants will have the baseline assessment battery (0) completed over the phone or online via REDCap with an Optum coach or OSU study team member before they are randomized to a study group; , follow-up assessments calls and mailing of JUUL pods and NRT will be conducted by [name] staff at the Ohio State University. Follow-up assessments will be conducted at +8 and +12 weeks.

Baseline Phase (Randomization)

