At the first visit, JUUL participants will be provided instructions on how to use the product and asked to attempt to completely switch to the product for the next 8 weeks so that we can accurately assess the use of the products on their health. Consistent with our previous EC switching studies,^{75,107} participants will be asked how they intend to completely switch to the product and asked about concerns they have about switching. Optum coaches will help participants address any reported barriers to switching to assist them in remaining switched over the 8-week period. Study staff will provide participants trouble-shooting tips for the mechanics of their product, provide replacement parts as needed, and also address adverse events as they arise (though <2% and mild in our team's previous EC studies).

Protocol Adherence and Quality Control

Data Management

Switching to a Vaping Device: Evaluating Risk Reduction among Quitline Treatment Failures

All data collection will follow HIPAA guidelines. Data will be collected directly from the participant by a research assistant or RIU coach. Data will include participant responses to computer-based, smartphone/EMA-based, and phone based survey questionnaires. All participants will be asked for an iCO sample daily for 12 weeks. A total of approximately 84 iCO samples will be collected from a single participant not to exceed 90 samples for any individual within the 12 week period.

Access to Identifiable Information and Data Storage: Only research assistants who have completed training in the ethical conduct of research and the study PI ([name]) will have access to individually identifiable private information about human subjects. All data will be treated as confidential and will never be stored or reported in association with identifying information. Participants will be consented verbally or electronically and mailed a hard copy of the consent. A common identification number will link identifiable forms (consent forms and contact information) and study-related data. Computer entered data will be de-identified and password protected.

Quality Assurance

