study phones at the end of the EMA period of the study. Participants will receive the final payment for completing EMAs when the study phone is received by research staff. **Bedfont iCO smokerlyzer monitor** will measure daily CO levels and biochemically confirm smoking abstinence over the course of the 3-month study. Participants will be prompted to connect the iCO device to the study smartphone each day following completion of the EMA and follow step-by-step directions to complete the CO test (see Figures 3 and 4). Results of these tests will be date and time stamped and saved. Participants will not receive feedback on test results. Our CO criteria for abstinence is consistent with numerous other studies using cutoffs of ≤ 6 ppm.¹²⁹⁻¹³⁴ As ECs do not produce CO, expired CO is a valid indicator of smoking status (i.e., switching completely to ECs) and compares favorably with cotinine and other biochemical measures that have longer detection windows.¹³⁵⁻¹³⁸ Self-reports of abstinence combined with facial recognition and CO levels suggestive of recent abstinence provide an accurate, immediate, and practical measure of abstinence. We have validated the iCO against the Vitalograph CO monitor, and our mHealth core has already integrated the iCO device into our platform. The manufacturer indicates that the iCO is valid for approximately 200 CO tests and has a sensor sensitivity of 1 ppm.¹³⁹ Our protocol will require no more than 90 CO testing sessions; well within the defined valid use range.

[figure not shown]

Figure 4. Bedfont iCO monitor completion steps.

Figure 3. Connected Bedfont iCO monitor.

Table 2. Measures

Measure	Baseline (0)	Product Trial (+8 weeks)	Surveillance (+12 weeks)	EMA ASSESSMENTS
Sociodemographic & Socioenvironment	x			Daily 90 days
Cig Dependence Scale	x			Daily Diary EMAs*
Product Use Status	x			# Cigarettes Smoked
Product Use - NRT	x			# Vaping Sessions
JUUL Use Evaluation		x	x	Other tobacco use
NRT Use Evaluation		x	x	EC product info
JUUL Expectancies – Cig		x	x	MNWS
JUUL Expectancies – Ecig		x	x	E-liquid Used
NRT Expectancies		x	x*	iCO Assessment
MNWS		x	x	Random EMAs
QSU cig		x	x	Affect/Mood/Stress
QSU ecig		x	x	Urge to Smoke
QSU NRT		x	x	Urge to Vape

Switching to a Vaping Device: Evaluating Risk Reduction among Quitline Treatment Failures

Adverse Events		x	x	Recency of Smoking
Ecig Dependence Scale		x	x	Recency of Vaping
NRT Dependence Scale		x	x	Social setting/Location
SRNT		x	x	Abstinence Self-Efficacy

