b) Risk of using e-cigarettes: The risk of side effects and adverse events are very low. These products are sold online, and at e-cigarette specialty stores and convenience stores nationwide, without a prescription. Nevertheless, all participants will be screened for general medical precautions (pregnancy, cardiovascular disease) and monitored for adverse events during the study period. Study personnel will assess for adverse events via self-report at all follow-up visits. Smokers will also be provided a study smartphone with a direct line to report an adverse event between follow-up visits. Any Serious Adverse Events will be reported to the study's medical monitor and then to the OSU IRB and to NIDA. We will withdraw participants who have a Serious Adverse Event, or become pregnant or begin to breastfeed. The most likely adverse (potential for nicotine overdose) event is anticipated to be rare (<5% in our team's previous studies) and mild (nausea, headache, disrupted sleep), and will be handled quickly (i.e., advice to participant to reduce or stop EC use). Lab studies of toxin exposure suggest that ECs incur no greater risk to health than do conventional cigarettes. Indeed, e-cigarettes generally show lower levels of harmful and potentially harmful constituents. To date, five e-cigarette studies discuss adverse events (3 survey and 2 randomized clinical trials), reporting mild and tolerable side effects that generally resolved completely over time with continued use (90% of cases); the most predominant of which were mouth/throat irritation, cough, and headache. In both randomized clinical trials, no Serious

Switching to a Vaping Device: Evaluating Risk Reduction among Quitline Treatment Failures

Adverse Events were reported and the e-cigarette group and the nicotine patch group had comparable levels of adverse events. The most common were mouth irritation, throat irritation, dry cough and headache.

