All observed or volunteered adverse events regardless of treatment group or suspected causal relationship to study product will be recorded on the adverse event page(s) of the Adverse Event Form. For the purpose of this study, hereafter Study Product will be used to refer to e-cigarettes. Events involving adverse Study Product reactions or illnesses with onset during the study should be recorded. Exacerbation of pre-existing illness is defined as a manifestation (sign or symptom) of the illness that indicates a significant increase in the severity of the illness as compared to the severity noted at the start of the trial. It may include worsening or increase in severity of signs or symptoms of the illness, increase in frequency of signs and symptoms of an intermittent illness, or the appearance of a new manifestation/complication. Exacerbation of a pre-existing illness should be considered when a patient/subject requires new or additional concomitant medication or non-medication therapy for the treatment of that illness during the trial. Lack of or insufficient clinical response, benefit, efficacy, therapeutic effect, or pharmacologic action should not be recorded as an adverse event. The medical monitor will be responsible for distinguishing between exacerbation of pre-existing illness and lack of therapeutic efficacy. For all adverse events, the PI will pursue and obtain information adequate both to determine the outcome of the adverse event and to assess whether it meets the criteria for classification as a Serious Adverse Event requiring immediate notification to the medical monitor. For all adverse events, sufficient information should be obtained by the PI to determine the causality of the adverse event (i.e., Study Product or other illness). The PI is required to assess causality and indicate that assessment on the Case Report Form. Follow-up of the adverse event, after the date of therapy discontinuation, is required if the adverse event or its sequelae persist. Follow-up is required until the event or its sequelae resolve or stabilize at a level acceptable to the investigator or his/her designated representative.

Serious Adverse Events

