Preventing and Limiting Adverse Events

We will monitor for risk of using e-cigarettes and NRT by screening participants for general medical precautions. The most likely adverse event (potential for nicotine overdose) is anticipated to be rare and mild based on the PI's previous studies, and will be handled quickly (i.e., advice to participant to reduce or eliminate nicotine use). Lab studies of toxin exposure suggest that e-cigarettes incur no greater risk to health than do combustible cigarettes. The PI and study personnel will be available for any questions that participants may have about e-cigarettes, NRT, smoking, or smoking cessation. Participants will be provided a study phone and data plan at no cost, to contact study personnel at any time. Any adverse events, breaks of confidentiality, or any other data or safety issues that arise will be discussed immediately between study personnel and the PI.

Collection of Adverse Events

The collection of adverse events will be on a self-report basis and logged within an electronic data capture system (REDCap) or collected using standardized paper forms and will only be identified with the study's ID of the participant.

Adverse Event Reporting Timelines

- All intervention staff are required to notify the PI of any Serious Adverse Events immediately.
- All Serious Adverse Events will be reported immediately to the medical monitor who will determine their severity and appropriate action or response.
- In accordance with current standard procedure, the PI will notify the OSU IRB of all Serious Adverse Events within 24 hours.
- In accordance with new policy and procedure, the PI will notify the National Institutes of Drug Abuse of all Serious Adverse Events within 72 hours.
- All Non-serious AEs will be reviewed weekly by the medical monitor or PI, for categorization and possible action.

Switching to a Vaping Device: Evaluating Risk Reduction among Quitline Treatment Failures

I. Literature Cited

1. CDC. Vital Signs: Current Cigarette Smoking Among Adults Aged \geq 18 Years—United States, 2005–2010. In: MMWR, ed.2011.
2. Treating tobacco use and dependence: 2008 update. Clinical Practice Guidline. 2008. at [http://www.ahrq.gov/clinic/tobacco/treating_tobacco_use08.pdf.'\).](http://www.ahrq.gov/clinic/tobacco/treating_tobacco_use08.pdf.)

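### No adverse-event question is scheduled before week 8, so capture during the 8 weeks of supplied product rests on unsolicited reports

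*Combined protocol and SAP*

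**What the plan says.** **When AEs are asked about.** Section G.7 (a) for NRT and (b) for e-cigarettes use the same sentence: "Study personnel will assess for adverse events via self-report at all follow-up visits". Section D.2 (Baseline and Follow-up Assessments) gives the dates: "Follow-up assessments will be conducted at +8 and +12 weeks". In Table 2 the columns after baseline read "Product Trial (+8 weeks) Surveillance (+12 weeks) EMA ASSESSMENTS" and the row reads "Adverse Events x x Recency of Smoking". The two marks are at +8 and +12 weeks, the baseline cell is empty, and the last entry is an unrelated item in the EMA column.

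**What happens with AEs.** Section G.7 expects the most likely event, nicotine overdose, to be rare, mild and dealt with promptly by advice. Section H.2 (Adverse Event Reporting Timelines) adds: "All Non-serious AEs will be reviewed weekly by the medical monitor or PI, for categorization and possible action".

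**Routes before week 8.** All participants get a study phone with a direct line for reporting events (G.7). Under JUUL Education and Counseling (D.2), staff "also address adverse events as they arise".

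**Other scheduled contacts.** In the JUUL arm, coaches ask about usage at the two later calls "to help determine if the quantity of the study product that was mailed to the participant should be increased or decreased". Section H.1 says self-report measures are taken at the coach calls but does not list them. Table 2 places the MNWS in the daily diary.

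**Reference level.** Section H.2 judges worsening of a pre-existing illness by its severity "as compared to the severity noted at the start of the trial".

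**The concern.** Prompt handling and weekly review only work if events are known soon after they occur. On the written schedule, the first time every participant is asked about AEs is the week in which supply ends. Until then an event reaches the review only if the participant reports it or a staff member happens to learn of it.

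Mild events are the most exposed to this. Section G.7 (b) cites earlier studies in which side effects mostly resolved with continued use (90% of cases). It gives no time to resolution, but any event that resolves before week 8 has to be remembered and volunteered at that visit. People who drop out before week 8 may never be asked. Without a recorded starting level, a smoker's existing cough or headache is hard to tell from a new or worse one. What is at stake is the completeness and timeliness of the safety record during exposure, in both arms.

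**Working it through.** The plan states no figure to reproduce, so the check is a reconciliation of the schedule.

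**1. Scheduled contacts and AE questions**

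| Day | Contact | AE question | Other symptom content |
|---|---|---|---|
| 0 | Baseline battery, first coach call | None (Table 2 cell empty) | None marked in Table 2 |
| 7 or 14 | Second coach call | None named | Self-report measures, content not listed (H.1) |
| 28 | Third coach call | None named | Same |
| 0 to 56, daily | Two EMAs, one of them the evening diary | None listed | MNWS in the diary (Table 2) |
| 56 | +8-week battery | Yes | MNWS |
| 84 | +12-week battery | Yes | MNWS |

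Supply runs for 8 × 7 = 56 days. Scheduled AE questions before day 56: 0. The longest interval without one is 56 days, the whole supply period. The text on the Randomized Product Trial Phase counts the time-0 battery among the follow-up batteries. Reading it that way adds no question during exposure, because time 0 precedes product use.

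The second coach call is at +1 week in D.1 but at +14 days in D.2 and H.1, hence the two values in the table.

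**2. What the daily MNWS can and cannot supply**

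There are 56 evening diaries in the supply period (2 × 56 = 112 EMAs in all; the plan says about 120). Section D.3 describes a 15-item scale that includes sleep problems, nausea, constipation, sore throat, dizziness and coughing. Compared with the plan's own lists:

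- Signs expected with the most likely event (G.7 b): nausea and disrupted sleep are covered, headache is not. 2 of 3.
- Nicotine overdose symptoms (G.7 c): nausea and dizziness are covered; vomiting, headache and rapid heart rate are not. 2 of 5.
- Most common e-cigarette complaints (G.7 b): throat irritation and cough are covered; mouth irritation and headache are not. 2 of 4.

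The items are framed as withdrawal, Table 2 leaves the MNWS cell empty at baseline, and no section sends diary scores to AE identification or to the weekly review.

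**3. Participants who may never be asked**

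Inputs from Section E.1: 420 randomised, 20% attrition. 0.20 × 420 = 84. This is a ceiling at that rate and assumes that all loss precedes week 8; the plan does not say when losses occur. E.1's final sample of 300 would instead imply 420 − 300 = 120 lost, which does not agree with 20%. The stated rate is used here.

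**4. Effect of adding the two later coach calls**

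With the second call at day 14, the intervals up to week 8 are 14, 14 and 28 days. With it at day 7 they are 7, 21 and 28 days. Either way the longest interval falls from 56 to 28 days.

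**The case against.** The plan has more in place during exposure than the AE row alone suggests, and a reader could easily infer too much from that row.

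- **That there are no scheduled data during exposure.** Not supported. The diary MNWS asks daily about several relevant symptoms in both arms, and coach calls collect self-report measures. AE questions at those calls are neither specified nor excluded.
- **That early events go unmonitored or cannot be acted on.** Not supported. Every participant has the direct line and can reach staff at any time. Events that arise are to be discussed at once with the principal investigator (H.2). Section G.7 (f) gives everyone a tip sheet on signs of nicotine overdose and poison-control numbers.
- **That the weekly review would be empty.** Not so. It receives volunteered events and, with recruitment over 12 months, the week-8 and week-12 reports of earlier enrollees.
- **That the comparison of AEs between arms is biased.** Not shown. Section E specifies no such comparison, both arms get three calls and the same phone and EMAs, and G.7 uses near-identical AE wording for each product. Troubleshooting and reactive AE handling are described only under JUUL, which is a reason for a common script and not evidence of bias.

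The baseline point also needs care. Table 2 leaves the MNWS, urge scales, timeline follow-back and iCO empty at baseline, although Section E.2 adjusts for baseline values, so that column may simply be incomplete. Eligibility screening does record cardiac, psychiatric, allergy and pregnancy status.

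All of this narrows the consequence. It does not supply a scheduled AE question before week 8, or a stated route from the existing symptom data to the review.

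**Conclusion.** The gap is real but limited. Followed exactly, the plan asks no scheduled AE question for 56 days, the full period of supplied product, and leaves capture in that time to volunteered or reactive reports. Mild, self-resolving events may be under-captured or recalled over up to 8 weeks; the documents do not allow the shortfall to be quantified. At most 84 of 420 participants could leave without a scheduled AE question. That figure rests on the 20% rate and on all loss occurring before week 8. It would be lower with later losses, or where the efforts in Section E.3 to reach people who drop out succeed. Such participants could still have volunteered events.

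Table 2 shows no recorded starting level for symptoms, although H.2 relies on one. The conclusion assumes that the unlisted coach-call measures contain no AE question; if they do, the plan should say so. This is a worthwhile, cheap improvement to safety capture. It does not show that events go unhandled or that either arm is favoured.

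**What to change.** 1. Add one short AE checklist at baseline and at the two later coach calls, and keep it at +8 and +12 weeks. Use the same script and timing in both arms. The baseline entry should record existing symptoms, so that worsening can be judged as H.2 requires.
2. Add these time points to the Adverse Events row of Table 2.
3. State in H.2 that checklist entries and the daily MNWS somatic items go to the weekly review, and who passes them on.
4. List the self-report measures taken at the coach calls (H.1).
5. Reconcile the timing of the second coach call: +1 week in D.1, +14 days in D.2 and H.1.

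The clinical or supply response to a reported event remains the sponsor's decision and is not part of this change.

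The cost is a few minutes per call and more non-serious AEs to log and review. All the contacts already exist.

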Sociodemographic data will assess participant age, sex, marital status, ethnicity, employment status, occupation, years of education, and socioeconomic status. Tobacco use history will assess years of smoking, age of smoking onset, average number of cigarettes per day, number and recency of previous 24-hour quit attempts, number of smokers in the household, prior use of nicotine replacement therapy and other stop smoking medications, and history of receiving smoking cessation counseling, and cigarette and EC expectance effects. It will also assess tobacco type, brand, frequency, quantity, and duration of use all of nicotine/tobacco products including cigars, cigarillos, little cigars, pipe tobacco, chewing tobacco, snuff, snus, EC, combustible tobacco hookah, and dissolvable tobacco. Complete Substitution will be defined as ≥7 days with no more than 1 conventional cigarette smoked (assessed via EMAs), daily exhaled carbon monoxide of ≤6 ppm as measured by iCO (see biomarker measures below), and reported use of ECs over the same 7-day period.

Switching to a Vaping Device: Evaluating Risk Reduction among Quitline Treatment Failures

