Switching to a Vaping Device: Evaluating Risk Reduction among Quitline Treatment Failures

Aim 1: The focus of aim 1 is the examination of differential levels of (Hyp 1a) substitution between JUUL and NRT, and (Hyp 1b) reported nicotine craving, withdrawal symptoms, number of cigarettes smoked per day, product abuse liability, and nicotine dependence, between JUUL and NRT. *Hypothesis 1a:* Complete substitution rates, at the 8 and 12 week follow-ups, will be compared between JUUL and NRT arms using logistic regression analysis, adjusting for baseline variables such as age, gender, number of cigarettes per day and/or randomization stratification factors. The GEE model will be performed for the repeated measure analysis of complete substitution rate across multiple visits. *Hypothesis 1b:* If needed, we will apply a normalizing transformation to the response measure (e.g., taking the logarithm of cigarettes per day) before proceeding with the analysis, as a means of removing the effects of potential outliers. We will examine changes in each outcome over time across the two groups using linear mixed model (LMM) regression analysis. We will employ a random intercept or slope parameter, as appropriate, and model the covariance structure for the repeated outcome measures, while accounting for baseline value of the outcome and potential confounders (including any variables not equally distributed between groups). Modeling is done using a likelihood-based approach and thus makes use of all available data (on the intention-to-treat (ITT) sample) to produce consistent estimates of the regression parameters. Contrast estimates comparing group effects over time will be used as measure of effect. A similar approach will be used to explore the EMA data collected.

Aim 2: The focus of aim 2 is the examination of changes in a biomarker of toxicant exposure. *Hypothesis 2:* We will examine changes in iCO, a biomarker of toxicant exposure, and EMA data using the methods outlined in Hypothesis.

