Aim 3: The focus of aim 3 is (Hyp 3a) to determine which EC device characteristics and perceived effects are associated with complete (vs. partial or no) substitution. *Hypothesis 3a:* We will examine whether changes in EC device characteristics and perceived effects obtained by EMA over time differ between those who achieve complete (vs. partial or no) substitution using linear mixed model (LMM) regression analysis. We will employ a random intercept or slope parameter, as appropriate, and model the covariance structure for the repeated outcome measures, while accounting for potential confounders. We will use similar methods to explore return to smoking in those who report complete substitution at any time during the study.

3. Missing Data

In the event of missing data, we will contact participants immediately. If a participant drops out, we will attempt to gather follow-up information by calling the study phone and trying to reach the participant through other provided contact information. However, if a participant refuses to be contacted or loses contact with the investigators, we will censor data at point of loss. Two statistical approaches will be used to handle missing data. First, we will use inverse probability weighting with propensity scores. This is a two-step procedure in which we first model the probability of missingness as a function of baseline covariates and previous outcomes. Next, the inverse of the resulting predicted probabilities (from the logistic regression model) will serve as weights in our proposed model of the response. We will compare these results to a more conservative ITT approach as a final step.

Switching to a Vaping Device: Evaluating Risk Reduction among Quitline Treatment Failures

F. Gender/Minority/Pediatric Inclusion for Research

1. Inclusion of Women and Minorities

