The research protocol calls for current smokers who recently failed to quit smoking using the standard QL program, to attempt to completely substitute JUUL or NRT. E-cigarettes are no more harmful than conventional cigarettes, and there is some evidence that that may offer reduced harm. Questionnaires and the exhaled breath collection procedure is non-invasive and involves minimal risk to study participants. Potential risks are as follows: a) risk of using NRT, b) risk of using e-cigarettes, c) dual use of cigarettes and e-cigarettes, d) loss of confidentiality or privacy, e) potential for undermining smoking cessation, and f) lack of appropriate storage of nicotine-containing products in a house with children and pets.

7. Protections Against Risk

Efforts to reduce risk are as follows:

a) Risk of using the NRT: The risk of side effects and adverse events is very low. These products are FDA-approved for smoking cessation, and sold at convenience stores nationwide, without a prescription. Nevertheless, participants will be screened for general medical precautions (pregnancy, cardiovascular disease), and all participants will be monitored for adverse events during the study period. Study personnel will assess for adverse events via self-report at all follow-up visits. Smokers will also be provided a study smartphone with a direct line to report an adverse event between follow-up visits. Any Serious Adverse Events will be reported to the study's medical monitor and then to the OSU IRB and to NIDA. We will withdraw participants who have a Serious Adverse Event, or become pregnant or begin to breastfeed. The most likely adverse event (potential for nicotine overdose) is anticipated to be rare (<5% in our team's previous studies) and mild (nausea, headache, disrupted sleep), and will be handled quickly (i.e., advice to participant to reduce or stop NRT use).

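### The rule to withdraw participants after an SAE, pregnancy or breastfeeding is not limited to study product and, read plainly, ends scheduled outcome follow-up when only product needs to stop

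*Combined protocol and SAP*

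**What the plan says.** Section G.7 (Protections Against Risk) gives the same sentence under a) for NRT and b) for e-cigarettes: "We will withdraw participants who have a Serious Adverse Event, or become pregnant or begin to breastfeed". Later in each paragraph, the mild overdose-type event is handled with product wording; in b) this is "advice to participant to reduce or stop EC use".

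Other parts of the protocol that bear on the rule:

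- Section H.2 counts an inpatient hospitalisation as serious and requires SAEs to be reported whatever their suspected relationship to product. It also requires a persisting adverse event to be followed after therapy is discontinued.
- Section G.6 (Potential Risks): "Questionnaires and the exhaled breath collection procedure is non-invasive and involves minimal risk to study participants".
- Sections D.1 and D.2 (Surveillance Phase) assess everyone in weeks 9-12 with no product supplied, and give tracking of later adverse events as one purpose of that phase.
- Section D.3 (Measures) makes complete substitution depend partly on "reported use of ECs over the same 7-day period".
- Section E.3 (Missing Data) opens with a general commitment to contact participants at once when data are missing. It continues: "If a participant drops out, we will attempt to gather follow-up information by calling the study phone". Censoring applies "if a participant refuses to be contacted or loses contact with the investigators, we will censor data at point of loss". The weights "model the probability of missingness as a function of baseline covariates and previous outcomes", and the results are compared with a more conservative ITT approach that is not defined.

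**The concern.** An SAE or a pregnancy may be a good reason to stop supplying nicotine. It is not by itself a reason to stop telephone questionnaires, a diary and a breath test. If the rule ends participation, the trial loses three things.

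1. **Primary-outcome status.** A JUUL participant who stops product and uses no other EC is a known non-substituter if followed to week 8. If withdrawn before then, the same person has a missing outcome. The weighting model uses baseline covariates and earlier outcomes, not the triggering event, so it does not represent this mechanism. If the conservative ITT analysis means that missing counts as not substituted, it would classify these people as follow-up would; the text does not say so.
2. **Secondary outcomes.** Cigarettes per day and iCO after withdrawal are no longer collected on schedule, although section E.2 intends to model these outcomes on the ITT sample with all available data.
3. **Safety information.** The triggering event is still followed under section H.2. New events through week 12, which are collected by self-report at follow-up contacts, would be detected less reliably in people who have just had a serious event or become pregnant.

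**Working it through.** **What the text settles.** Four places could limit the rule or keep these participants in follow-up.

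| Place | What it provides | Keeps scheduled assessments going? |
|---|---|---|
| G.7 a) and b) | Withdraws participants; product wording is used only for the mild event | No; not limited to product |
| H.2 | Follow-up of the event after therapy stops | Only for that event |
| E.3 | Contact when data are missing; pursuit of those who drop out; censoring of those who refuse or are lost | Not clearly; participants whom the study withdraws are not mentioned |
| E.2, Hypothesis 1b | ITT sample, all available data | No; it analyses what exists and does not require collection |

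**Inputs.** Section E.1 gives 35% (JUUL), 20% (NRT), two-sided 0.05, 420 enrolled, 186 per group, 20% attrition and 300 analysed. It names a chi-squared test for the power statement and Fisher's exact test for the week 8 comparison. The documents give no rate of SAE, pregnancy or breastfeeding. I assume 1-5% for illustration, which has no source: 0.01 × 420 = 4.2 and 0.05 × 420 = 21, so 4 to 21 people.

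**Reproducing the plan's power.** With n per arm and p̄ = (0.35 + 0.20)/2 = 0.275,

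power = Φ{[0.15 − 1.96·√(2p̄(1−p̄)/n)] / √[(0.35·0.65 + 0.20·0.80)/n]}.

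At n = 150 this is Φ[(0.15 − 0.1011)/0.0508] = 83.2%. Fisher's exact test, by full enumeration at 150 per arm, gives 80.3%. Both agree with the plan's claim of more than 80%.

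**Power if all 4 to 21 were additional losses.** The plan's 420, 186 per group and 300 do not fit together, so three starting points are shown: 300 as stated, 420 × 0.8 = 336, and 2 × 186 × 0.8 = 297.6, rounded to 298.

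| Start | Chi-squared, none lost | 4 lost | 21 lost |
|---|---|---|---|
| 300 | 83.2% | 82.7% (296) | 80.5% (279) |
| 336 | 87.2% | 86.8% (332) | 85.0% (315) |
| 298 | 83.0% | 82.5% (294) | 80.2% (277) |

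Fisher's exact test from 300: 80.3%, then 79.6% (148 per arm), then 78.0% (140 JUUL, 139 NRT). Exact power is not smooth in n: with 139 JUUL and 140 NRT the last figure is 79.6%. From 336, Fisher's power is 84.7%, and 83.2% after losing 21.

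**Classification.** Suppose a fraction w of each arm is withdrawn before week 8 and would have counted as not substituted, and the rest substitute at 35% and 20%. The definition names only EC use, so counting the NRT cases as not substituted is itself an assumption.

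- Followed: JUUL 0.35(1−w), NRT 0.20(1−w), difference 0.15(1−w).
- Omitted: JUUL 0.35, NRT 0.20, difference 0.15.

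| w | JUUL followed | NRT followed | Difference followed | Shift in the difference if omitted |
|---|---|---|---|---|
| 1% | 34.65% | 19.80% | 14.85 points | 15 − 14.85 = 0.15 |
| 5% | 33.25% | 19.00% | 14.25 points | 15 − 14.25 = 0.75 |

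In the JUUL arm alone, omission raises the rate by 35 − 34.65 = 0.35 to 35 − 33.25 = 1.75 points.

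**The case against.** The sentence sits under the headings for product-use risks, so its authors may have meant withdrawal from product. The protocol elsewhere separates stopping product from ending contact: it advises stopping NRT or EC after mild events without mentioning study exit, follows adverse events after therapy ends, and assesses everyone without product in weeks 9-12. Section E.3 opens with a commitment to contact participants about missing data that has no exception for study-initiated withdrawal, and a reachable person with an SAE neither refuses contact nor is lost. Cigarettes per day could then be recovered by telephone, since the timeline follow-back is in the week 8 and 12 batteries. The consent pages, which may state withdrawal terms, were not available.

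Much of this stands. A reader might infer that the protocol orders all assessments to stop, or that cigarettes per day and iCO are lost whichever missing-data method is used. The documents support neither. What remains is that no visible text clearly keeps these participants on the assessment schedule, and a call prompted by missing data does not replace a daily diary and daily iCO.

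Numbers are also likely to be low. Section G.7 reports no SAEs in two earlier randomised trials. Section D.2 excludes recent cardiac events and stroke, pregnancy, planned pregnancy within three months and breastfeeding. That also stands, and it limits the point's weight.

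**Conclusion.** The point holds as a low-priority, inexpensive improvement. Read plainly, the rule discards outcome and safety data after randomisation with no added protection, because stopping product already gives the protection.

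The illustrative effect is small: 0.15-0.75 points on the JUUL-NRT difference, under an unsourced 1-5% in both arms, all before week 8 and all counted as not substituted. The 0.35-1.75 points in the JUUL arm alone should not be read as the shift in the treatment contrast, because the same rule applies to both arms.

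Two opposite inferences on power should be avoided. Power does not stay above 80% in every case: from 300, Fisher's exact test falls to 79.6%-78.0%. Nor does this show that the trial is underpowered: some or all of these losses may fall within the 20% attrition allowance, and from 336 Fisher's power is still 83.2% after losing 21. The documents also give no evidence that these withdrawals would differ between arms, so a directional bias from differential withdrawal cannot be claimed.

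**What to change.** Reword the sentence in both G.7 a) and G.7 b), for example:

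*Study product will be stopped if a participant has a Serious Adverse Event, becomes pregnant or starts breastfeeding. Unless consent is withdrawn, the participant stays in the study.*

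Then state that such participants continue the diary, iCO, the week 8 and week 12 assessments and adverse event follow-up, and are analysed in their randomised arm. Record product discontinuation, with date and reason, separately from study withdrawal.

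This wording still stops product for any SAE, related or not. That is a separate safety choice, which the sponsor may keep.

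The cost is minor protocol and consent wording, one data field, and a few extra contacts with participants who have stopped product. The change has to be in place before such cases arise, because diary and iCO data that were not collected cannot be recovered later.
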